2.2.2 KNOWN POTENTIAL BENEFITS

Acupuncture has been shown to be a safe and effective treatment for several patient populations. Although there is less evidence for individuals with MG, acupuncture treatment may improve quality of life and activities of daily living.

2.2.3 ASSESSMENT OF POTENTIAL RISKS AND BENEFITS

We believe the potential risks to the participants in this study are minimal and that the benefit of understanding whether acupuncture treatment improves quality of life and activities of daily living in patients with MG outweighs the potential risks.

3 OBJECTIVES AND ENDPOINTS

OBJECTIVES	ENDPOINTS
Primary	
To determine the effect of acupuncture on quality of life in patients with MG.	MG-QOL15
Secondary	
To determine the effect of acupuncture on activities of daily living in patients with MG.	MG ADL

4 STUDY DESIGN

4.1 OVERALL DESIGN

Study Design:

This study is an unblinded, controlled randomized, 2-arm clinical trial.

Hypotheses:

Primary Hypothesis: We hypothesize that acupuncture will improve the quality of life in MG patients.

Secondary Hypothesis: We hypothesize that acupuncture will improve activities of daily living in MG patients.

Randomization:

Prior to the first acupuncture treatment visit, participants will be randomized into two treatment groups. Randomization is explained in **Section 6.3**.

Acupuncture Treatment Groups:

Group 1: 10 participants will receive acupuncture treatment immediately 2x per week for 12 weeks = 24 total.

Group 2: After a 12-week delay, 10 participants will receive acupuncture treatment 2x per week for 12 weeks = 24 total.

Study Intervention:

Acupuncture treatment will consist of a standardized treatment protocol designed for this study. Approximately 23-32 needles will be inserted into specific areas of the body for a duration of 30 minutes. Additional details of the treatment are discussed in **Section 6.1**.

4.2 SCIENTIFIC RATIONALE FOR STUDY DESIGN

Justification for an unblinded study: Because it will be clear to both study personnel and participants who will have a delayed start and who will start immediately, neither will be blinded in this study. This will be reported as a limitation of the study.

Justification for an uncontrolled study with no control group: N/A

4.3 JUSTIFICATION FOR INTERVENTION

Acupuncture is a treatment that has been practiced for over 4,000 years and is well-accepted by many cultures. Although the mechanism is not well understood, acupuncture has been shown to be safe and effective for treating several conditions (e.g. headaches, chronic pain). The purpose of this study is to determine whether acupuncture treatment can improve quality of life and activities of daily living in patients with MG.

4.4 END-OF-STUDY DEFINITION

A participant is considered to have completed the study if he or she has completed study treatment visits and assessments. The end of the study is defined as completion of the last post-treatment visit for each group.

5 STUDY POPULATION

5.1 INCLUSION CRITERIA

In order to be eligible to participate in this study, an individual must meet all of the following criteria:

- Ability to provide and provision of signed and dated informed consent form
- Age 18-80
- Diagnosis of MG

5.2 EXCLUSION CRITERIA

An individual who meets any of the following criteria will be excluded from participation in this study:

- Non-English speaking
- Participation in acupuncture treatment outside of the study, while enrolled
- History of any other serious neurological, psychiatric, chronic pain disorders, or seizures
- History of bleeding diathesis, other bleeding disorders, or syncope with needle puncture
- Recent or active substance use disorder
- Women who are currently pregnant, lactating, or planning to become pregnant during the study
- Any other medical conditions that could affect their ability to participate in acupuncture treatments for the study duration (as determined by study investigators)
- Active participation or past participation ≤ 3 months in any other interventional study.
- Unwilling to participate in all study related activities

5.3 LIFESTYLE CONSIDERATIONS

N/A

5.4 SCREEN FAILURES

Pre-screening Phone Call:

All potential participants will undergo a pre-screening phone call to determine whether they meet the inclusion/exclusion criteria. Patients will be considered ineligible if they do not meet one or more of the inclusion/exclusion criteria during pre-screening. We will collect information on why participants are ineligible or decide not to move forward with the trial.

Pre-treatment Visit:

Screen failures are defined as participants who are considered eligible during the pre-screening phone call, but it was subsequently determined that they do not meet one or more of the inclusion/exclusion criteria at or after the Pre-treatment (baseline) visit. We will collect information on why participants screen fail or decide not to move forward with the trial.

Rescreening Patients:

Individuals who do not meet the criteria for participation in this trial (ineligible or screen failure) because of meeting one or more exclusion criteria that are likely to change over time may be rescreened up to one time. Examples include: successful treatment for a substance use disorder; women who are no longer

pregnant, lactating, or planning to become pregnant; or participation in an interventional study ≥ 3 months prior. Rescreened participants will be assigned a new participant number.

5.5 STRATEGIES FOR RECRUITMENT AND RETENTION

Recruitment: Individuals with MG will be recruited by physician and therapist referrals from HealthPartners' clinics. We will also advertise our research study by distributing flyers to HealthPartners' physicians and throughout HealthPartners' clinics. Recruitment flyers will also be provided to our community partners for example, the Minnesota Brain Injury Alliance, TRIA, and Allina Health. If we encounter difficulties with recruitment, we plan to submit an amendment to the IRB to contact HealthPartners and Park Nicollet patients and members and invite them to participate.

To reach our target enrollment, we anticipate that we will need to screen 60 people, of those 30 individuals will sign the informed consent, and of those 25 individuals will be randomized to treatment groups.

Remuneration: Participants will be provided gift cards totaling \$50 per person for completing certain time points of the research study. Group 1: Will receive a \$25 gift card after all acupuncture treatments and surveys were completed, and another \$25 gift card after the last post treatment visit, if all surveys were completed. Group 2: Will receive a \$25 gift card after half of the acupuncture treatments have been completed and surveys were completed, and another \$25 after the post-treatment visit, if all surveys were completed.

6 STUDY INTERVENTION(S) OR EXPERIMENTAL MANIPULATION(S)

6.1 STUDY INTERVENTION(S) OR EXPERIMENTAL MANIPULATION(S) ADMINISTRATION

6.1.1 STUDY INTERVENTION OR EXPERIMENTAL MANIPULATION DESCRIPTION

The study intervention for both groups is acupuncture treatment. Acupuncture is a treatment where fine needles are inserted into specific areas of the body to achieve a therapeutic benefit. The treatment regimen is described next in more detail.

6.1.2 ADMINISTRATION AND/OR DOSING

Acupuncture Treatment Methods:

Group 1 will receive twice-weekly acupuncture immediately over 12-weeks. After a 12-week delay, Group 2 will also receive twice-weekly acupuncture over 12-weeks. Acupuncture treatments will be separated by a minimum of 2 days and a maximum of 14 days, unless a participant has an illness, such as COVID-19. In this case, additional time may be allowed, as determined by the investigator. Treatment methods will be identical for both groups and are described below.

Standard, sterile stainless-steel, disposable needles (DongBang™ Corporation, Spring Ten 0.22 x 30mm; Boryeoung, Republic of Korea) will be inserted in the acupuncture point locations (described below), with approximately 23-32 needles used for each treatment session. The number of needles used will be based

on the patient-reported symptoms. The depth of the needle insertion will be approximately 10-20mm, depending on the region of the body undergoing treatment. Needle reaction (soreness, numbness or distended feeling around the point, also known as a Deqi sensation) will occur during the initial insertion. Following 10 minutes of retention, some of the needles will be rotated in order to maintain Deqi sensation. Maintaining Deqi sensation has been shown to increase the effectiveness of acupuncture.^{10,11} All needles will be left in place for a total of 30 minutes, which is a typical duration in acupuncture practice.

Acupuncture points were selected for their classical Traditional Chinese Medicine indications relevant to MG symptom pathology, as well as their modern biomedical muscular, immunological, and neurological actions. The anatomical location for each point will be based on the World Health Organization's acupuncture point guideline.¹² Traditional Chinese manual acupuncture will be used at up to 32 acupuncture points. During treatment, acupuncture needles can be removed due to extreme pain or discomfort, so as not to exceed the removal of more than 4 needles.

6.2 FIDELITY

6.2.1 INTERVENTIONIST TRAINING AND TRACKING

Acupuncturists:

Acupuncture treatments will be administered by MN licensed acupuncturists with a Master's degree level of training in acupuncture (or higher) from accredited institutions, and five or more years of clinical experience. Prior to enrolling participants, the acupuncturists will complete practice sessions together of the treatment protocol and methods of administration to ensure consistency between providers.

Training:

Following IRB approval and prior to recruitment and enrollment, the study acupuncturists will complete at least 1 practice session each. For the training, we will seek volunteers who will sign a volunteer consent form prior to participating. The purpose of training will be to ensure consistency in intervention procedures and further standardized treatment methods. This includes, but is not limited to: needle location, needle depth, time of first and last needle placement, and total treatment duration.

Tracking:

All practice sessions will be documented on a training log. This will include dates and times of the trainings, names of the volunteers, and printed names and signatures of the study acupuncturists. We will also keep a record of the volunteers' signed treatment release forms.

6.3 MEASURES TO MINIMIZE BIAS: RANDOMIZATION AND BLINDING

Randomization:

Randomization will be performed with a 1:1 allocation ratio. Balanced treatment assignments will be achieved using permuted block randomization with random block sizes stratified by gender. This decision was based on evidence that females in this population reported higher rates of headaches.¹³ The study biostatistician will generate a randomization schedule using the SURVEYSELECT procedure in SAS. Assignments will not be seen by other study personnel in advance and will not be changed after randomization.

Blinding:

Study personnel will be unblinded to the randomization, as it will be clear the number of participants who have a 12-week delay and those who do not. In addition, it will be clear to participants which treatment group they are in and it will be impossible to blind them from this information.

6.4 STUDY INTERVENTION/EXPERIMENTAL MANIPULATION ADHERENCE

Participants will be asked to adhere to study visits and to complete study assessments. Participants will remain active unless withdrawn from the study (see **Section 7**). We will track participants' adherence to study visits, as well as completion of the assessments. These will be documented in the relevant eCRF.

6.5 CONCOMITANT THERAPY

For this protocol, participants may use non-opioid analgesics for pain control, including over-the-counter medications and dietary supplements, and prescribed medications. This includes use for rescue therapy in the event of exacerbation of symptoms due to acupuncture treatment. Medication usage will be assessed at each study visit and documented in the relevant eCRF.

6.5.1 RESCUE THERAPY

See section 6.5 (above).

7 STUDY INTERVENTION/EXPERIMENTAL MANIPULATION DISCONTINUATION AND PARTICIPANT DISCONTINUATION/WITHDRAWAL

7.1 DISCONTINUATION OF STUDY INTERVENTION/EXPERIMENTAL MANIPULATION

When a participant who signed the consent form chooses to discontinue participation in the study or study intervention, or if the principal investigator and co-investigators determine that a participant should discontinue participation, they will be withdrawn from the study. A withdrawal will either be defined as 'Patient Withdrawal' or 'Principal Investigator Withdrawal'. The participant will be asked to complete an early withdrawal phone call 7-14 days from the date the intervention was discontinued. The purpose of the phone call will be to record any AEs or serious adverse events (SAEs) that may have occurred after the discontinuation of treatment. Research staff will attempt to call the participant up to 3 times.

The data that will be collected at the time of study withdrawal will include the following:

- The reason(s) for discontinuation of the study intervention

The data that will be collected during the early withdrawal phone call will include the following:

- AEs or SAEs that occurred since the time of withdrawal

7.2 PARTICIPANT DISCONTINUATION/WITHDRAWAL FROM THE STUDY

Participants are free to withdraw from participation in the study at any time upon request. An investigator may discontinue a participant from the study for the following reasons:

1. Participant has not completed an acupuncture treatment for > 14 days, unless a participant has an illness, such as COVID-19. In this case, additional time may be allowed, as determined by the investigator.
2. Significant study intervention non-compliance
3. Lost-to-follow up; unable to contact subject (see **Section 7.3, Lost to Follow-Up**)
4. Any event or medical condition or situation occurs such that continued collection of follow-up study data would not be in the best interest of the participant or might require an additional treatment that would confound the interpretation of the study
5. The participant meets an exclusion criterion (either newly developed or not previously recognized) that precludes further study participation

The reason for participant discontinuation or withdrawal from the study will be recorded on the relevant eCRF. Subjects who sign the informed consent form and are randomized but do not receive the study intervention may be replaced. Subjects who sign the informed consent form, and are randomized and receive the study intervention, and subsequently withdraw, or are discontinued from the study, will not be replaced.

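### Stopping acupuncture ends study follow-up (7.1, and at discretion 7.2) and 9.4.2 analyses only those with a 12-week score, so the promised intention-to-treat analysis can leave out people who stopped treatment

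*Combined protocol and SAP*

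**What the plan says.** Section 7.1 covers a participant who "chooses to discontinue participation in the study or study intervention". It gives the consequence in the same sentence, jointly with the case of a decision by the study team: "if the principal investigator and co-investigators determine that a participant should discontinue participation, they will be withdrawn from the study". For a participant who chooses to stop, the rule is automatic, and stopping the intervention alone is enough.

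Section 7.2 is discretionary: "An investigator may discontinue a participant from the study for the following reasons". Item 1 is "Participant has not completed an acupuncture treatment for > 14 days", with an exception for illness. Item 2 is "Significant study intervention non-compliance". Item 4 includes a situation that "might require an additional treatment that would confound the interpretation of the study". Item 5 is meeting an exclusion criterion. On replacement: "Subjects who sign the informed consent form and are randomized but do not receive the study intervention may be replaced". Those who started and then left are not replaced.

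After withdrawal: "The participant will be asked to complete an early withdrawal phone call 7-14 days from the date the intervention was discontinued". Section 7.1 lists only adverse events for that call. The visit description in 1.3 also has MG-QOL15 and MG ADL taken then.

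Sections 9.3 and 9.4.2 promise intention-to-treat, and 9.4.2 says this holds whatever treatment was actually received. Section 9.4.2 also restricts the final analysis to participants with both the pre-treatment and the 12-week assessment. Its only response to substantial missing data is a comparison of baseline characteristics.

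**The concern.** An intention-to-treat comparison needs the week-12 outcome of everyone randomised, including those who stopped. Here the event that makes treatment depart from plan also ends outcome collection, and the analysis rule then removes the person.

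Group 2 has no acupuncture to stop, miss or fail to comply with before week 12, so those grounds can remove people from Group 1 only. The discretionary decisions under 7.2 are taken by staff who know the allocation (6.3). People who stop, or who need other treatment, may differ in their 12-week change. A baseline comparison can describe who was lost, but it cannot recover their outcomes. Section 9.2 considers dropout, withdrawal and missing data only as a loss of power.

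**Working it through.** **1. Following one participant through the text.** A Group 1 participant decides at the end of week 3 to stop acupuncture. Section 7.1 withdraws them. The call comes 7-14 days later, at week 4-5. No section provides a week-12 assessment after withdrawal, so 9.4.2 leaves them out. The call falls at week 12 only for someone who stops around week 10-11.

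**2. What item 1 takes to trigger.** With two fixed treatment days a week, 2 to 5 days apart, three consecutive missed sessions leave a gap of exactly 14 days. Four leave 14 + 2 to 14 + 5 = 16-19 days, which exceeds the limit. Four of 24 sessions is 17%.

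**3. The plan's own power figures (9.2).** Two-sided two-sample t-test, alpha 0.05, noncentrality d/√(1/n₁ + 1/n₂), n₁ + n₂ − 2 degrees of freedom.
- 10 v 10, d = 1.32: noncentrality 1.32/√0.2 = 2.95, power 79.7% (stated 80%).
- d = 9.5/7 = 1.357: N = 20, 81.8% (stated 82%); N = 18, 77.1% (77%); N = 16, 71.4% (71%).

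These reproduce. At the same effect, loss from one arm only gives 79.5% (9 v 10), 76.6% (8 v 10) and 68.6% (6 v 10). Losing four from one arm thus costs little more power than the 71% already disclosed for a loss of four. What 9.2 does not address is bias.

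**4. Possible bias, as an illustration.** From 9.2: 10 per arm and SD 7. Assumed: no true effect, baseline-change correlation r of 0 to 0.5, and k people removed from one arm. The analysis is ANCOVA of change on arm and baseline, with 100,000 simulated trials per case. The signal that leads to removal has correlation ρ with the 12-week change.

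| Removed from one arm | Shift (points) | Type I error |
|---|---|---|
| Any number, unrelated to outcome (ρ = 0) | 0 | about 5% |
| One, at random from the worse half | 0.4-0.6 | 5.0% |
| Two, at random from the worse half | 1.0-1.3 | about 6% |
| One, worst signal, ρ = 0.5 | 0.5-0.6 | about 5.5% |
| One, worst signal, ρ = 1 | 0.9-1.2 | about 7% |
| Two, worst signal, ρ = 0.5 | 0.8-1.1 | about 6% |
| Two, worst signal, ρ = 1 | 1.7-2.2 | about 10-11% |

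Hand check at r = 0, ρ = 1: the two lowest of 10 standard normal values have expected values −1.539 and −1.001. Removing one shifts the arm mean by 7 × 1.539/9 = 1.20 points. Removing two shifts it by 7 × (1.539 + 1.001)/8 = 2.22 points. At ρ = 0.5 these halve to 0.60 and 1.11.

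Against the 9.5-point planning effect, 0.4-2.2 points is 4-23%. The standard error of the difference is 7 × √(2/10) = 3.1 points. The sign reverses if Group 2 loses the people, and equal selective removal from both arms gives no shift.

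**The case against.** The strongest reply is that the plan is milder than it first looks, and much of that reply stands.

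- A reader might infer that missed sessions or added treatment lead automatically to withdrawal. They do not: 7.2 is discretionary and exempts illness, and 7.3 tells staff to reschedule missed visits. Only the 7.1 rule for a participant who chooses to stop is automatic. Sections 6.5, 8.1 and 9.4.9 allow, track and compare medication, so a drug change alone is probably not meant to end participation.
- A reader might infer that poor attenders are all gone before the per-protocol analysis in 9.3. The documents point the other way. Section 9.3 expects some to remain in the main analysis, and 9.4.9 plans a sensitivity analysis without participants who had long illness-related delays.
- A reader might infer that replacement hides the losses. Anyone who started acupuncture is not replaced, so the rule does not reach the main scenario here.
- A reader might infer that the bias favours acupuncture. That would follow if those lost from Group 1 were doing worse. It would reverse if they stopped because they felt well, or if worsening controls were removed under item 4. Item 5 could also remove a control who has outside acupuncture, which 5.2 excludes.
- The early-withdrawal call does collect MG-QOL15 under 1.3, and 9.4.2 computes change from each person's first two scores, which could admit it. The 12-week requirement in the same section points to exclusion. If the score were admitted, it would mix outcomes from different times in Group 1.

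None of this supplies a week-12 score for a person who stops.

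**Conclusion.** The point holds in this form. Through the automatic rule in 7.1 and the discretionary grounds in 7.2, stopping treatment can end outcome collection, and 9.4.2 then analyses only those with a 12-week score. For people who stopped before week 12, that contradicts the intention-to-treat promise, and the grounds tied to acupuncture can act on Group 1 only.

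The textual conflict needs no assumption. The size does: how many are lost, from which arm, and how strongly loss tracks outcome. The documents give no rate for these rules; the 20% loss in 9.2 is a planning scenario. The 11% type I error needs the two worst 12-week changers to be exactly the ones removed, before that change has been observed. The softer cases leave type I error at 5-6% and shift the estimate by less than half a standard error. The change is worth making because the outcomes cannot be recovered later and, at 10 per arm, each person is a tenth of a group.

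**What to change.** - **7.1 and 7.2 items 1, 2 and 5:** make these grounds for stopping acupuncture only. In item 4, remove the confounding-treatment ground for ending follow-up and keep the best-interest ground. Align 8.3.9, so that pregnancy during treatment stops acupuncture but not follow-up.
- **Week-12 assessment:** anyone who stops acupuncture and still consents has MG-QOL15 and MG ADL taken by the existing phone interview 12 weeks after the start of the first period. Participants still in treatment keep Post-treatment Visit 1 as scheduled, because a fixed call could catch slower attenders mid-course and move the primary time point.
- **9.4.2:** state that these week-12 scores enter the intention-to-treat ANCOVA whatever treatment was received. State that early-withdrawal-call scores do not replace them in the primary analysis and are used only in a sensitivity analysis when no week-12 score exists. Call the remaining analysis set complete-case.

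The cost is wording in four sections and one call of about 20 minutes per affected participant, with no new instruments. The estimate will then include the effect of stopping, so it may be smaller. Anyone who refuses or cannot be reached is still missing, and the plan should say so.

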- Duration: Approximately 20 minutes via phone
- Research staff will:
 - Complete the Medication Review short form in the relevant electronic case report forms (eCRFs) in Research Electronic Data Capture (REDCap), a secure web-based system.
 - Interview patients using the MG-QOL15 and MG ADL surveys and document in REDCap.

4. Study Intervention (Groups 1 & 2)

- Duration: Each visit approximately 1 hour
- A study acupuncturist will:
 - Complete the Adverse Events (AE) Reporting, Medication Review, and Treatment Adherence in the relevant eCRFs in REDCap.
 - Perform the acupuncture treatment.

5. Post-treatment Visit 1 (Groups 1 & 2)

- Duration: Approximately 20 minutes via phone
- Research staff will:
 - Complete the AE Reporting and Medication Review forms in the relevant eCRFs in REDCap.
 - Interview patients using the Symptom Severity Scale (from the treatment log), MG-QOL15, and MG ADL surveys and document in REDCap.
 - Ask qualitative survey questions about the participant's experience with acupuncture.

6. Post-treatment Visit 2 (Group 1 only)

- Duration: Approximately 20 minutes via phone
- Research staff will:

- Complete the AE Reporting and Medication Review forms in the relevant eCRFs in REDCap.
- Interview patients using the Symptom Severity Scale (from the treatment log), MG-QOL15, and MG ADL surveys and document in REDCap.
- Ask qualitative survey questions about the participant's experience with acupuncture.

7. 2-week follow up call (Group 2 only)

- Duration: Approximately 5 minutes via phone
- Research staff will:
 - Complete the AE Reporting in the relevant eCRFs in REDCap.

8. Early Withdrawal Call (for individuals who withdraw from the study early)

- Duration: Approximately 20 minutes via phone
- Research staff will:
 - Complete the AE Reporting and Medication Review forms in the relevant eCRFs in REDCap.
 - Interview patients using the Symptom Severity Scale (from the treatment log), MG-QOL15, and MG ADL surveys and document in REDCap. Ask qualitative survey questions about the participant's experience with acupuncture.

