9.4.2 ANALYSIS OF THE PRIMARY ENDPOINT(S)

The MG-QOL15 scores will be collected for each participant at several time points. The primary outcome, change in MG-QOL15 scores over the first 12-weeks, will be calculated using the first and second collected scores for both groups. Group 1 will have received the full acupuncture intervention between the two measurements while Group 2 will act as the untreated control. We will present the mean change by group with corresponding standard deviations. Analysis of covariances (ANCOVA) with adjustment for baseline MG-QOL15 and covariates identified above will be used to determine if a significant ($p<0.05$) intervention effect is present. If the model identifies a significant difference in change of MG-QOL15 associated with acupuncture treatment, next steps will assess if this change is still present 12-weeks after completing the full acupuncture treatment. Using data from Group 1, a paired t-test will be used to compare the MG-QOL15 scores directly after treatment (Post-treatment Assessment 1) and scores 12-weeks post-treatment (Post-treatment Assessment 2). (Refer to Schema on page 4 for data collection points.)

Prior to analysis, we will plot our outcomes to examine their distribution and decide whether we should consider non-parametric analyses. Only subjects with complete data from both pre-treatment assessment and 12-week assessment will be included in the final analysis. Data will be analyzed per an intent-to-treat approach regardless of actual treatment received. If a large proportion of missing data is noted, we will compare baseline characteristics of subjects who completed the treatment with those who were lost to follow-up.

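### A waiting-list control who takes up outside acupuncture can be discontinued and lost from the primary analysis, against the stated intention-to-treat rule

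*Combined protocol and SAP*

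**What the plan says.** - Section 5.2 lists among the exclusion criteria "Participation in acupuncture treatment outside of the study, while enrolled". As worded, it can be met only after enrolment.
- Section 7.2 opens with "An investigator may discontinue a participant from the study for the following reasons", and reason 5 is "The participant meets an exclusion criterion (either newly developed or not previously recognized) that precludes further study participation".
- Section 7.1 gives the consequence when the investigators "determine that a participant should discontinue participation, they will be withdrawn from the study". It describes no status of being off treatment but still followed.
- For the early withdrawal call, section 7.1 lists only "AEs or SAEs that occurred since the time of withdrawal". The visit description in section 1.3 says of the same call: "Interview patients using the Symptom Severity Scale (from the treatment log), MG-QOL15, and MG ADL surveys and document in REDCap". Section 7.1 times the call 7-14 days after the intervention was discontinued.
- Section 7.2 adds: "Subjects who sign the informed consent form and are randomized but do not receive the study intervention may be replaced". Participants who have been treated and then leave are not replaced.
- Section 9.3 puts all analyses on an intention-to-treat basis, and section 9.4.2 says "Data will be analyzed per an intent-to-treat approach regardless of actual treatment received". The same paragraph of 9.4.2 restricts the final analysis to people with both the pre-treatment and the 12-week assessment.

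**The concern.** A control who obtains acupuncture elsewhere is exactly the case that an analysis regardless of treatment received is meant to cover. Read together, the withdrawal and complete-data rules allow that person to disappear from the comparison instead.

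The route is unlikely to act equally on the two arms. In weeks 0-12 Group 1 is given acupuncture twice a week, while Group 2 has volunteered for acupuncture, knows its allocation and must wait. It is a reasonable inference, though not a documented rate, that outside use would fall mainly in Group 2. The replacement rule adds a second asymmetry: a waiting control has not yet been treated and can be swapped out, whereas a treated Group 1 participant cannot.

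At stake is whether the primary comparison remains one between the groups as randomised. With 10 per group, each lost control is a tenth of the comparator.

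**Working it through.** **The chain of rules, for a Group 2 participant in weeks 0-12**

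1. The participant has outside acupuncture and so meets the 5.2 criterion.
2. It is newly developed, so 7.2 reason 5 is available to the investigator.
3. If it is used, 7.1 makes it a withdrawal from the study.
4. The only later contact is the early withdrawal call. Sections 7.1 and 1.3 disagree on whether it records MG-QOL15. Its timing is not tied to week 12, and its starting date is undefined for someone who has had no study intervention to discontinue.
5. Without a 12-week assessment, the 9.4.2 complete-data rule leaves the person out.
6. Being untreated, the person may be replaced under 7.2.

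**Reproducing the planning figure**

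Inputs from section 9.2: 10 per group, two-sided two-sample t-test, alpha 0.05, difference d = 1.32 SD. Power comes from the noncentral t distribution with n1 + n2 − 2 degrees of freedom and noncentrality d / √(1/n1 + 1/n2). For 10 v 10 the noncentrality is 1.32 / √0.2 = 2.95, and power is 79.7%, against the stated 80%.

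**Illustration: k of 10 controls lost and not replaced**

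The documents give no uptake rate; k = 1 or 2 is an assumption.

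*Loss unrelated to outcome.* The expected difference stays at 1.32 SD.
- k = 1 (10 v 9): power 77.3%.
- k = 2 (10 v 8): power 74.3%.

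*Loss of exactly the worst-changing controls.* This was simulated with 100,000 trials, normal changes and a true difference of 1.32 SD.
- k = 1: mean difference 1.15 SD, power 69.8%.
- k = 2: mean difference 1.00 SD, power 57.9%.

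If the lost controls would have done worse than average by m SD, the remaining control mean moves by k·m/(10 − k) SD. The simulated shifts are 1.32 − 1.15 = 0.17 SD and 1.32 − 1.00 = 0.32 SD. They imply m = 0.17 × 9/1 ≈ 1.5 SD and m = 0.32 × 8/2 ≈ 1.3 SD, so this is an extreme case. At the SD of 7 in the section 9.2 table, the shifts are 0.17 × 7 = 1.2 and 0.32 × 7 = 2.2 points.

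**What keeping them costs**

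Suppose k randomly chosen controls use outside acupuncture, each gains the full 1.32 SD, and all are analysed as randomised. With f = k/10, the difference is 1.32 × (1 − f). The control variance becomes 1 + f(1 − f) × 1.32², and it is averaged with the treated variance of 1.
- k = 1: difference 1.19 SD, power about 68%.
- k = 2: difference 1.06 SD, power about 55%.

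Under this assumption, keeping them gives less power than losing them at random (77% and 74%).

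These figures use the t-test of section 9.2. Section 9.4.2 names ANCOVA, whose power also depends on a baseline correlation that the plan does not give.

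**The case against.** **The route may seldom operate in time.** Discontinuation is discretionary, and reason 5 requires that the criterion preclude further participation. Group 2 has no scheduled contact between Visit 1 and Pre-treatment Visit 2, and no described form asks about outside acupuncture. Use would often surface, if at all, in the same call that records the 12-week score, when both scores are in hand. This stands: it limits frequency but does not close the route for someone who reports use earlier.

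**A score may exist.** Section 1.3 has the early withdrawal call collect MG-QOL15, and 9.4.2 computes change from the first and second collected scores. But 7.1 lists only adverse events for that call, and 9.4.2 also requires a 12-week assessment. The passages conflict, so neither the loss nor the retention of a usable score can be taken as settled.

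**Section 7.2 deletes nobody from the analysis.** Correct. The loss arises from 7.1 and the complete-data rule, which apply to every reason for withdrawal; some of those, such as missed treatments, fall on Group 1 in weeks 0-12. What singles out this reason is that its trigger is receipt of a treatment other than the one assigned, which 9.4.2 expressly says should not matter.

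**Direction and size.** A reader might infer that controls who worsen are the ones who seek acupuncture, so that removal flatters the waiting group and shrinks the effect. The documents do not support that. If uptake is unrelated to outcome there is no bias. If the removed controls benefited from outside acupuncture, removal enlarges the difference relative to intention-to-treat. Nor are 1.15 SD with 70% power and 1.00 SD with 58% power expected values; they need the loss to fall on exactly the worst changers. Replacement, for which section 9.2 raises enrolment to 25, could restore the numbers, but not the group as randomised.

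**Conclusion.** The point holds as an inconsistency between rules. Sections 5.2, 7.1, 7.2 and the complete-data rule in 9.4.2 together allow a randomised control to leave the primary analysis because of treatment received, which 9.3 and 9.4.2 say will not happen. It is a possibility under the plan, not a certainty.

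Its frequency and the direction of any bias cannot be determined from the documents. For an assumed 1 or 2 of 10 controls lost without replacement, the consequence runs from power alone (77% and 74%) to an attenuated estimate of 1.15 or 1.00 SD with power of 70% or 58%. These are bounds for the two selection patterns shown, not a forecast. A reader might also infer that keeping such participants would recover power. It need not: under full benefit to randomly chosen users, power is about 68% or 55%. The case for change rests on validity and on agreement with the plan's own intention-to-treat statement.

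**What to change.** 1. State that outside acupuncture after randomisation is recorded as a protocol deviation and does not by itself end outcome collection.
2. State that the week-12 MG-QOL15 and MG ADL are still sought from such a participant and analysed in the randomised group, and that any replacement is additional and does not displace that person.
3. Confine exclusion for outside use to the per-protocol sensitivity analysis. Section 9.3 currently triggers that analysis only by poor attendance, so its definition needs the addition.
4. Add one yes/no question on outside acupuncture to Pre-treatment Visit 2 and Post-treatment Visit 1.
5. Reconcile the visit description in 1.3 with 5.2, 7.1, 7.2 and 9.4.2, including what the early withdrawal call collects and when it takes place for someone not yet treated.

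Whether such a person goes on to receive study acupuncture is a separate matter for the investigators, and this change does not touch it.

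The cost is a short amendment and one question in two existing calls. The statistical price is that contaminated controls stay in the comparison and dilute it, as quantified above.
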